16.4.2.2 Haemostatic effect

Description of the haemostatic effect of N8-GP when used for treatment of bleeding episodes will be summarised and listed according to the four point scale for haemostatic response (none, moderate, good and excellent).

A success rate will be calculated based on counting good or excellent as successes and none and moderate as failures, and based only on reported outcomes.

For the calculation of the success rate the numerator will include all treated bleeding episodes with a reported haemostatic response of good or excellent, while the denominator will include all treated bleeding episodes with a reported haemostatic response. A sensitivity analysis will also be conducted where the denominator also includes treated bleeding episodes with missing response (i.e., missing response is counted as a failure).

Protocol v 1 | 94 of 114

EudraCT No.: 2013-004025-88

 Protocol
 Date:
 04 November 2013
 Novo Nordisk

 Trial ID: NN7088-3908
 Version:
 1.0

 UTN: U1111-1148-1897
 Status:
 Final

Page:

95 of 114

Haemostatic effect will be determined based on haemostatic response for bleeding episodes occurring both during pre-prophylaxis and prophylaxis period.

Haemostatic response will also be summarised by type of bleeding.

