8.2.3 Treatment of bleeding episodes in inhibitor patients

Bleeding episodes in inhibitor patients that do not respond sufficiently to N8-GP treatment may be treated with by-passing agents according to local practice.

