Multiple bleeding locations occurring from the same event (e.g., due to a fall) or at the same time point will be counted as one bleeding episode.

of 114 Protocol v 1 92

Protocol Date: 04 November 2013 Novo Nordisk Version: 1.0

All bleeding endpoints will be evaluated based on bleeding episodes treated with N8-GP unless the bleeding was considered clinically insignificant (non-treatment requiring bleeding episode) and the associated treatment given was part of prophylaxis.

Patients initiating ITI treatment will for the statistical analyses be considered like withdrawals and data collected during ITI treatment period will be summarised and reported separately. Evaluation of these data will be considered exploratory only.

If necessary, a statistical analysis plan (SAP) may be written in addition to the protocol, including a more technical and detailed elaboration of the statistical analyses. If created, the SAP will be finalised before the first database lock.

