5.3.6 Treatment of patients with FVIII inhibitors

Patients who develop FVIII inhibitors during this trial may receive N8-GP and/or Treatment of bleeding episodes with by-passing agents, e.g. i.e. rFVIIa or APCC for treatment of bleeding episodes according to local standard care is allowed for patients who develop FVIII inhibitors within this trial. However, N8-GP dose levels used should not exceed 75 U/kg as a single dose and not exceed 200 U/kg as a maximum 24 hour dose. Treatment with FVIII concentrates other than N8-GP is not allowed. By-passing agents are not considered trial medication.

The ultimate goal of treatment in patients with high-titre inhibitors is to permanently eradicate the inhibitor by immune tolerance induction therapy (ITI), thereby making it possible for the patient to be treated routinely with FVIII replacement therapy again. The therapeutic concept is based on long-term uninterrupted high exposure to FVIII in an effort to sufficiently tolerise the immune system. In that state, the clinical responsiveness to FVIII replacement therapy is restored.

Novo Nordisk plans that Patients who develop inhibitors, within this trial, will be offered continued treatment with N8-GP, including ITI for a maximum of 24 months. ITI with N8-GP will not be initiated until Novo Nordisk has reviewed the clinical data available after completion of the N8-GP pivotal and surgery trial (pathfinderTM2 and pathfinderTM3), and of the paediatric PTP trial (pathfinderTM5) data needed for opening the paediatric PUP trial according to EMA requirements.

It is expected to use a N8-GP dosing regimen for ITI similar to local standard care/guidelines applied for ITI with marketed FVIII products. For each individual patient, ITI regimens with N8-GP would have to be reviewed by the investigator every month, and more formally reviewed every 3 months by Novo Nordisk.

If patients with (usually low titre) inhibitors respond well to treatment with N8-GP then the patient can continue the prophylaxis. These patients can still start ITI treatment within 6 months after the

Protocol Amendment
Trial ID: NN7088-3908

CONFIDENTIAL

Date: 20 March 2015 | Novo Nordisk
Version: 2.0

UTN: U1111-1148-1897 CONFIDENTIAL Status: Final Page: 14 of 41

confirmatory inhibitor test. If the inhibitor is still present (BU>/=0.6) at 6 months after the confirmatory test the patient must start ITI or withdraw from the trial.

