8.2.2 Concomitant medication

A **concomitant medication** is any medication including vaccination, other than the investigational medicinal product (N8-GP), which is taken during the trial until EOT. By-passing agents should also be listed as concomitant medication.

Protocol Amendment
Trial ID: NN7088-3908

CONFIDENTIAL

Date: 20 March 2015 | Novo Nordisk
Version: 2.0

Status:

Page:

Final

26 of 41

UTN: U1111-1148-1897 EudraCT No.: 2013-004025-88

Height at screening

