Patients initiating ITI treatment will for the statistical analyses be considered like withdrawals and data collected during ITI treatment period will be summarised and reported separately. Evaluation of these data will be considered exploratory only.

If necessary, a statistical analysis plan (SAP) may be written in addition to the protocol, including a more technical and detailed elaboration of the statistical analyses. If created, the SAP will be finalised

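### The haemostatic success rate has no rule for bleeds in which an inhibitor patient outside ITI also received a by-passing agent, so such a bleed can count as an N8-GP success

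*Combined protocol and SAP*

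**What the plan says.** **Which bleeds enter.** The opening text of Section 16 states: "All bleeding endpoints will be evaluated based on bleeding episodes treated with N8-GP unless the bleeding was considered clinically insignificant". The exception there concerns trivial bleeds covered by a prophylaxis dose. A bleed given only a by-passing agent is therefore out; a bleed given N8-GP and a by-passing agent is in.

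**How they are counted.** Under 16.4.2.2, "the numerator will include all treated bleeding episodes with a reported haemostatic response of good or excellent". *Moderate* and *none* are failures, and every treated bleed that has a rating goes into the denominator. The one planned sensitivity analysis concerns missing ratings. The endpoint draws on "bleeding episodes occurring both during pre-prophylaxis and prophylaxis period".

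**When a by-passing agent is allowed.** Section 8.2.3: "Bleeding episodes in inhibitor patients that do not respond sufficiently to N8-GP treatment may be treated with by-passing agents according to local practice". Section 5.3.6, as changed by Amendment 2, begins "Patients who develop FVIII inhibitors during this trial may receive N8-GP and/or" and goes on to by-passing agents for bleeds. Amendment 2 also adds to 8.2.2: "By-passing agents should also be listed as concomitant medication".

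**What is separated.** Section 16 provides that "Patients initiating ITI treatment will for the statistical analyses be considered like withdrawals", with ITI-period data reported separately. Section 5.1 calls inhibitor patients a separate cohort. Section 16.2 keeps every exposed patient in the full analysis set.

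**The concern.** The endpoint is meant to describe the effect of N8-GP on bleeds. It is one of the key supportive secondary endpoints chosen in 4.2.2 for public posting. Section 8.2.3 allows a by-passing agent when the response to N8-GP is not sufficient. If that agent then stops the bleed and the parent or investigator rates the outcome *good*, the plan credits the success to N8-GP.

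The patients concerned are those with inhibitors who are not on ITI: low-titre patients who stay on N8-GP, and patients in the period of up to 6 months between the confirmatory inhibitor test and the start of ITI (5.3.6 as amended). Section 11.6.2 expects inhibitors in about 30% of patients, so the group need not be small. These are also the patients in whom N8-GP is most likely to fall short, which is what a reader of the success rate would want to see.

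**Working it through.** The documents give no expected success rate and no count of bleeds treated with both products, so there is no plan figure to reproduce. The check has two parts.

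**1. Does any existing text remove these bleeds?**

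| Text | Effect on a bleed given both products outside ITI |
|---|---|
| Section 16, bleeds treated with N8-GP | Stays in |
| Section 16, ITI patients handled like withdrawals | Not affected; covers the ITI period only |
| 16.4.2.2, pre-prophylaxis and prophylaxis periods | Stays in; amended 5.3.6 lets inhibitor patients who respond continue prophylaxis |
| 5.1, separate cohort | Named, but Section 16 carries it out only for ITI |
| 6.4, withdrawal criterion 6 (other coagulation factors, unless related to ITI) | Conflicts with 5.3.6 and 8.2.3; even read literally, 6.4 and 17.2 let data collected before withdrawal be used |
| Table 8-1 | *Excellent* and *good* need improvement within about 8 hours of a single injection; the product is not named, the rating need not precede rescue, and *good* allows further injections |
| 8.6.1, bleed record | Lists N8-GP doses only, so the by-passing agent does not show there |

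None of these takes the bleed out of the main rate.

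**2. How far can the rate move?**

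Let f be the share of rated bleeds given both products, d the share of those rated *good* or *excellent*, and s the success rate in all other rated bleeds.

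- Planned rate: (1 − f)s + fd
- Rate with these bleeds counted as failures: (1 − f)s
- Rate with these bleeds excluded: s
- Planned minus failure-coded: fd, which is never negative and does not depend on s
- Planned minus excluded: f(d − s), which is negative when d is below s

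All three inputs are assumptions. With s = 90%:

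| f | d | Planned | Failures | Planned − failures (points) | Planned − excluded (points) |
|---|---|---|---|---|---|
| 1% | 0% | 89.1% | 89.1% | 0.0 | −0.9 |
| 1% | 50% | 89.6% | 89.1% | +0.5 | −0.4 |
| 1% | 100% | 90.1% | 89.1% | +1.0 | +0.1 |
| 5% | 0% | 85.5% | 85.5% | 0.0 | −4.5 |
| 5% | 50% | 88.0% | 85.5% | +2.5 | −2.0 |
| 5% | 100% | 90.5% | 85.5% | +5.0 | +0.5 |
| 10% | 0% | 81.0% | 81.0% | 0.0 | −9.0 |
| 10% | 50% | 86.0% | 81.0% | +5.0 | −4.0 |
| 10% | 100% | 91.0% | 81.0% | +10.0 | +1.0 |

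The excluded rate is 90.0% in every row. With s = 80% the fifth column is unchanged, and at f = 10% the last column runs from −8.0 to +2.0.

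**The case against.** The strongest reply is Table 8-1. A by-passing agent is allowed after an insufficient response to N8-GP, and a bleed with an insufficient response should rate *moderate* or *none*, both of which are failures. This stands in part. A rater who judges the first N8-GP injection alone will record most such bleeds as failures. But nothing tells the rater to do so, the rating at home is made by parents in the eDiary, and a by-passing agent given within the 8-hour window can shape what they see.

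Second, amended 5.3.6 speaks of what patients may receive, not of what one bleed may receive. That is fair. The support for both products in the same bleed comes from 8.2.3.

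Third, failure-coding is a choice. It would also fail bleeds in which a by-passing agent was given for some other reason, and rating before rescue or exclusion could also be defended. This stands, and is why the choice must be written down and a second analysis shown.

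Fourth, the stakes are modest: 16.4.1 has no confirmatory secondary endpoints, the analysis is descriptive, responses are also listed, and Section 16 foresees a possible SAP with more detail. All true. It lowers the weight of the point but does not close the gap.

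A reader might also infer that N8-GP consumption per bleed is understated because by-passing doses are left out. The documents do not support that: 4.2.2 and 16.4.2.4 define the endpoint as the amount of N8-GP, and by-passing doses are not N8-GP.

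**Conclusion.** The gap is real and limited. A bleed given both products in an inhibitor patient outside ITI enters the main success rate and counts as an N8-GP success if rated *good* or *excellent*. Against counting such bleeds as failures, the error is f × d and can run only in favour of N8-GP. Under the assumed ranges (f from 1 to 10%, d from 0 to 100%) it is 0 to 10 points, and it is zero if every such bleed is rated *moderate* or *none*.

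A reader might go further and infer that the success rate is inflated. The documents do not establish this. They give neither f nor d, Table 8-1 pulls d down, and against exclusion rather than failure-coding the planned rate may even be the lower of the two. What can be said is that the rate can be overstated and that the plan has no rule to prevent it. This is a change the sponsor should make, not a defect that undermines the trial.

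**What to change.** 1. In 16.4.2.2, count a bleed in which a by-passing agent or other factor product was given before the rating as an N8-GP failure in the main success rate.
2. Identify these bleeds by matching concomitant-medication records to the bleed record. Section 8.2.2 requires start and stop dates but not times, and the items listed in 8.6.1 include no time for the rating. Use times where recorded, and otherwise fix a date-matching convention before database lock.
3. Show the rate excluding these bleeds as a sensitivity analysis, with a note that exclusion may raise the rate because it can drop N8-GP failures.
4. State whether inhibitor patients outside ITI are in the main rate or only in the separate cohort of 5.1.
5. Reconcile withdrawal criterion 6 in 6.4 with 5.3.6 and 8.2.3, since together they determine which of these bleeds can occur outside ITI. Which clinical rule should hold is for the sponsor and its clinicians.

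The cost is some protocol or SAP wording and a programming link between two existing data sets, with no essential new data collection. The descriptive rate may become slightly less favourable, and some bleeds given a by-passing agent for other reasons will count as failures.

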16.4.2.3 Incidence of high titre inhibitors

The rate of high titre inhibitors (defined as inhibitor titre > 5BU) will be reported similar to the primary endpoint

16.4.2.4 FVIII consumption

Total amount of N8-GP used, amount of N8-GP used for prophylaxis (U/Kg/month/year) and amount consumed per bleeding episode (number of injections and U/Kg bw/bleeding episode) will be summarised and listed.

16.4.2.5 Safety endpoints

Adverse events including SAEs and MESI

Treatment emergent AEs (TEAEs, defined as AEs occurring after dosing with trial product) and treatment emergent SAEs (TESAEs) will be summarised by frequency of events and frequency of patients with any event. Similar summaries cross-classified by severity and by causal relation to trial produce will also be made.

MESIs will be summarised similarly to AEs.

Furthermore, listings will be provided displaying all TEAEs and TESAEs including pertinent clinical information.

All additional safety parameters such as laboratory parameters and physical examinations will be summarised and listed.

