4.2.2 Secondary Endpoint

- Frequency of Adverse events (AEs) including serious AEs and Medical Events of Special Interest (MESI).*
- Incidence of confirmed high titre inhibitors (defined as inhibitor titre > 5BU)*
- Number of breakthrough bleeding episodes during prophylaxis with N8-GP (annualised bleeding rate).*
- Haemostatic effect of N8-GP in treatment of bleeding episodes, assessed by a predefined 4-point haemostatic response scale ("excellent", "good", "moderate" and "none").*
- Consumption of N8-GP for prophylaxis (number of injections and U/Kg per month and per year)
- Consumption of N8-GP for treatment of bleeding episodes (number of injections and U/Kg required per bleeding episode)
- Total consumption of N8-GP per patient (prevention and treatment of bleeding episodes) per month and annualised value

Protocol v 1 | 24 of 114

^{*}Key supportive secondary endpoint prospectively selected for posting on clinicaltrials.gov

UTN: U1111-1148-1897 EudraCT No.: 2013-004025-88 Version: 1.0
Status: Final
Page: 25 of 114

5 Trial design

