5.2 Rationale for trial design

The trial design follows current standards for similar trials, and the EMA "Guideline on the clinical investigation of recombinant and human plasma-derived factor VIII products"⁷.

The trial design will provide information on safety and efficacy of N8-GP in paediatric PUPs below 6 years of age with severe haemophilia A (FVIII activity level of <1%).

The purpose of the present trial is to evaluate immunogenicity of N8-GP and to document the safety and efficacy of N8-GP in long-term prophylaxis and treatment of bleeding episodes in paediatric PUPs.

The main phase of the trial will generate safety and efficacy, aiming for a minimum of 50 EDs per patient. This number of EDs is required by the EMA guideline⁷ for evaluation of new FVIII products. The trial does not include a placebo control group, as it is considered unethical to administer an ineffective treatment to patients with haemophilia. An active control has not been included as extensive comparative data from recently registered rFVIII products are available in comparable global populations including patients from EU and US.^{14, 15} Furthermore, the EMA guideline does not require a comparison to neither placebo nor an active comparator.

There will be no randomisation due to the single-arm nature of the trial.

A multinational design has been chosen to ensure a sufficient screening pool of patients with this rare disorder, to meet local regulatory requirements and to reflect the anticipated patient population.

Protocol v 1 | 26 of 114

Figure 5–1 Patient flow chart

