Novo Nordisk will use the Global Haemophilia Network Investigator Portal to distribute and share trial-related documents and information with the participating sites.

The eDiary software and hardware implementation are compliant with the requirements of FDA 21 CFR Part 11 and ICH E6 (EU directive for personal data protection). After trial completion, each trial site will be supplied with long-life CDs. These CDs will contain site-specific patient records including the patient's eDiaries and audit trail including any data additions and corrections made on each form. The eDiary vendor will furthermore retain and securely store copies of all archived documents and data for 15 years or as required by local data retention laws for trial data.

Protocol v 1 91 of 114

04 November 2013 | Novo Nordisk Protocol Date: Trial ID: NN7088-3908 Version: 1.0 CONFIDENTIAL Final

Status:

92 of 114

Page:

UTN: U1111-1148-1897 EudraCT No.: 2013-004025-88

16

Statistical considerations

Novo Nordisk will be responsible for the statistical analysis.

The main statistical reporting of the trial will be performed when 50 patients have completed main phase (minimum 25 weeks) with at least 50 EDs and completed visit 9. EDs during ITI treatment will not count in the determination of when a patient has reached 50 EDs. Data from patients not yet having completed the main phase and data from patients that have entered extension phase at this point will be included up to latest visit prior to this cut-off date. This report will cover all endpoints, and will form the basis for the paediatric indication. The data will be presented for the main phase and for the extension phase separately as well as combined.

Except for the confidence interval for inhibitor rate and for annualised bleeding rate, the evaluation of data will be based on descriptive statistics, i.e. summary tables, listings and figures.

An updated reporting of the trial with supportive data will be performed when 100 patients have had at least 100 EDs. Data from all patients will be included up to latest visit prior this cut-off date. The data will be presented for the main + extension phase and the extended prophylaxis period (beyond 100 EDs) separately as well as combined.

All data, will be reported separately in a final report when the trial is completed.

[figure not shown]

Figure 16–1 Individual patient flow and time periods for trial reporting

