6.6.3 Rationale for withdrawal criteria

- Criteria nos. 1-6 are included to protect the patient's safety and reliability of the data.
- Criteria nos. 7-1012 are included to ensure appropriate treatment of inhibitor patients.

Protocol Amendment
Trial ID: NN7088-3908

CONFIDENTIAL

Date: 20 March 2015 | Novo Nordisk
Version: 2.0

7 Milestones

Planned duration of recruitment period (FPFV – LPFV): approximately 42 months

Planned FPFV: 26-Jun-2014 01 May 2014

Planned LPFV: 02 October 2020 02 Apr 2018

End of trial is defined as LPLV: 13 November 2021 13 May 2019

The duration of the trial for each individual country will vary. However, the end of trial will be no later than 13 May 2019 13 November 2021

The end of the clinical trial is defined as last visit of the last patient.

Planned completion of clinical trial report (CTR): November 2019 14 May 2022.

The duration of N8-GP treatment in the trial is a minimum total 100EDs for a particular patient. Once a patient has achieved 100EDs, they may be offered the option to continue in the trial until either N8-GP is commercially available in the relevant country or until the marketing authorisation application for N8-GP is rejected in the relevant country unless the N8-GP trial, part of the trial or a trial site is terminated by Novo Nordisk or a relevant authority for any reason. In any event, the LPLV for the trial will be no later than *13 November 2021* 30 June 2018 whether or not the product is commercially available in the relevant country.

8 Mathods and assessments

. . .

Fig 8-1: added to pre-prophylaxis box – Visits at: ED 5,10,15,20

• • •

Screening and enrolment log

. . . .

At screening, patients will be provided with a trial card stating that they are participating in a trial and giving contact address(es) and telephone number(s) of relevant trial site staff. Patient's parent(s)/LAR(s) should be instructed to return the trial card to the investigator at the last trial visit or to destroy the trial card after the last visit.

Each patient will be assigned a unique 6-digit number. It must be stated in the medical records that the patient is participating in the trial, including the patient number.

Protocol Amendment
Trial ID: NN7088-3908

CONJUDENTIAL

Date: 20 March 2015 | Novo Nordisk
Version: 2.0

Informed consent procedure

. . .

Informed consent for obtaining genotyping must be collected, if applicable. *Genotype consent is not applicable for Israel*.

. . . .

For withdrawn patients

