16.5 Interim reporting

[...]

An updated report will be made when the first 100 patients have had at least 100 EDs. A final report with supportive data will be made when all patients have completed both parts of the trial

[...]

A final report of the trial will be made after the LPLV cut-off on 13 November 2021. In case some ITI patients have not finished their treatment at the time of LPLV, an addendum to the final report will be made once the last ITI patient has completed the trial.

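### Adverse events are summarised without an exposure denominator, so crude figures cannot be read directly in combined tables, across reporting cut-offs or beyond 100 exposure days

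*Combined protocol and SAP*

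**What the plan says.** Section 4.2.2 lists "Frequency of Adverse events (AEs) including serious AEs and Medical Events of Special Interest (MESI") and marks it as a key supportive secondary endpoint. Section 16.4.2.5 gives the whole analysis. Treatment-emergent adverse events (TEAEs) and serious adverse events (TESAEs) "will be summarised by frequency of events and frequency of patients with any event", with further tables by severity and causality, and listings. For medical events of special interest (MESIs) it adds "MESIs will be summarised similarly to AEs".

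Section 16 says of the main report: "The data will be presented for the main phase and for the extension phase separately as well as combined". Patients still in the main phase at that cut-off, and those already past it, contribute data up to their latest visit. Section 16.5 as amended by Amendment 5 adds an interim evaluation, and Amendment 8 states: "A final report of the trial will be made after the LPLV cut-off on 13 November 2021".

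Three rules determine how long a patient can be observed:
- The safety analysis set takes every patient exposed to N8-GP (Section 16.2).
- Adverse events are collected until the end of trial visit (Section 11.2).
- Amendment 8 to Section 5.1 follows patients until last patient last visit (LPLV).

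Bleeding is treated differently. Section 16.4.2.1 models the bleeding count with adjustment for exposure time and explains why unequal durations need it.

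**The concern.** Event counts, and the share of patients with at least one event, both grow with time observed even when the underlying risk is constant. Here observation time varies by design. Entry is staggered over years while the closing date is fixed. Phases end at a number of EDs that patients reach at different speeds. Some patients may leave early, and those starting ITI are treated like withdrawals (Section 16).

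A reader who sees a higher percentage at a later cut-off, or in the combined column, cannot tell from the planned tables whether risk changed or follow-up lengthened. The plan recognises this problem for bleeding but does not carry the principle over to adverse events.

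**Working it through.** **1. The plan's own phase length.** Section 16 gives at least 25 weeks for the main phase; Section 5.3 gives at most 26 weeks at twice-weekly dosing. Fifty EDs at 3.5-day intervals: 50 × 3.5 / 7 = 25.0 weeks. This agrees.

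**2. Other intervals allowed in the main phase (Table 5–1).**
- Every 3rd day: 50 × 3 / 7 = 21.4 weeks.
- Every 7th day: 50 × 7 / 7 = 50 weeks.

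These figures assume continuous prophylaxis without extra doses for bleeds. Pre-prophylaxis, with more than a week between doses, lengthens the phase.

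**3. Calendar ceiling.** Inputs are from Section 7 as amended by Amendment 2 ("Planned FPFV: 26-Jun-2014" and "Planned LPFV: 02 October 2020") and from the LPLV date above.
- 26 June 2014 to 13 November 2021: 2,697 days / 365.25 = 7.38 years.
- 2 October 2020 to 13 November 2021: 407 days / 365.25 = 1.11 years.
- Ratio: 7.38 / 1.11 = 6.6, before any withdrawal.
- Lower end: one dosing day, which is enough to enter the safety set.

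**4. A second statement on duration.** The Summary as amended by Amendment 8 puts end of trial up to 4 years after the first patient's 100th ED. On continuous prophylaxis, 100 EDs take 100 × 3 / 365.25 = 0.82 years to 100 × 7 / 365.25 = 1.92 years. That implies a ceiling of about 4.8 to 5.9 years, so 5 years is used below as the long horizon.

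**5. Effect on the planned summary.** The documents give no adverse event rate, so the rate L is assumed constant over a range. Share of patients with any event after T years = 1 − exp(−L × T). T = 0.48 and 0.96 years correspond to 50 and 100 EDs at twice-weekly dosing.

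| L per patient-year | 0.48 y | 0.96 y | 5 y | 7.38 y |
|---|---|---|---|---|
| 0.05 | 2.4% | 4.7% | 22.1% | 30.9% |
| 0.1 | 4.7% | 9.2% | 39.3% | 52.2% |
| 0.5 | 21.3% | 38.1% | 91.8% | 97.5% |

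**6. What a rate would show.** Take 50 patients and L = 0.5.
- At 0.48 years: 50 × 0.48 × 0.5 = 12 events in 24 patient-years, or 0.50 per patient-year (exact Poisson 95% CI 0.26 to 0.87).
- At 5 years: 50 × 5 × 0.5 = 125 events in 250 patient-years, or 0.50 per patient-year (0.42 to 0.60).

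The count rises about tenfold and the percentage from 21% to 92%, while the rate is unchanged.

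**The case against.** The strongest reply is that the phases already standardise exposure. Visit 9 falls at ED 50 to 52 and visit 14 at ED 100 to 102, so a completer contributes about 50 EDs to each phase, and results are shown by phase. This stands for completers. It does not cover the combined column, patients still in a phase at a cut-off, early leavers or ITI starters. Nor does it cover time beyond 100 EDs, which Sections 5.3 and 8.1.8 describe as continued participation in the extension phase.

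Second, 7.4 years is a ceiling from planned dates, not typical exposure. First visit need not be first dose, continuation after 100 EDs is optional, and it can end when the product reaches the local market. This is correct.

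Third, patient-years are not the only sensible scale. An average over long follow-up can dilute early risk, and Amendment 8 itself reports low recovery within the first 5 EDs. Inhibitor formation, one of the MESIs, already has its own ED-based denominator in Section 16.3. This is a reason to keep the split by phase, not to leave out exposure.

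Fourth, an optional SAP might have specified rates, and recorded dates would allow them to be derived later. No such SAP is in the file, and a rate derived later is not a pre-specified one.

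A reader might also infer that adverse events cannot be compared with other products, because Section 5.2 says that "extensive comparative data from recently registered rFVIII products are available". The documents do not support that. The sentence justifies having no active control, and no comparison of adverse events with other products is planned.

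**Conclusion.** The point holds as a reporting weakness of minor severity. The planned adverse event summary has no exposure denominator. Crude counts and percentages are therefore not directly interpretable in combined tables, across successive cut-offs or beyond 100 EDs. For assumed constant rates of 0.05 to 0.5 per patient-year, the share with any event goes from 2.4–21% at 0.48 years to 22–92% at 5 years at unchanged risk.

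The size rests on the assumed rates, on a constant hazard and on everyone being followed for the full time shown; the real contrast depends on actual follow-up. A reader might infer that nothing can be compared between phases. That goes too far: for completers, exposure in EDs is roughly equal in the main phase and in the extension up to visit 14. What remains between them is calendar time, about 21 to 50 weeks for 50 EDs.

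**What to change.** In Section 16.4.2.5, for TEAEs, TESAEs and MESIs, add events per patient-year of exposure next to the counts and percentages, by phase and combined, at each reporting cut-off. Put total patient-years and total EDs in the column headings. Show ITI time separately, in line with the rule in Section 16 that patients starting ITI count as withdrawals and their ITI data are reported apart. State how time at risk starts and stops: for example, from first dose to the earliest of end of trial visit, ITI start and data cut-off.

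The cost is a few lines of text and one extra table column. Injection dates and times are already recorded (Section 8.5), and exposure time is already needed for the bleeding analysis. An average rate can hide early clustering of events, so the by-phase split should stay.
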